#### **7.4.1.1. Sensitivity Analysis of the Primary Endpoint – No Imputation for Missing Data**

The change from baseline eGFR for patients treated with bardoxolone methyl is compared with placebo at Week 12 using ANCOVA analysis with the following fixed factors: KDIGO strata (HEAT\_STRAT) and treatment group (TRT).

The ANCOVA analysis uses eGFR values collected in the Week 12 analysis window (Table 3). Missing Week 12 eGFR data are not imputed.

The difference between bardoxolone methyl and placebo in change from baseline of eGFR is estimated along with the 95% confidence interval at Week 12.

#### **7.4.1.2. Sensitivity Analysis of the Primary Endpoint – Imputation for Missing Data**

The change from baseline eGFR for patients treated with bardoxolone methyl is compared with placebo at Week 12 using ANCOVA analysis with the following fixed factors: KDIGO strata (HEAT\_STRAT) and treatment group (TRT).

The ANCOVA analysis uses eGFR values collected in the Week 12 analysis window (Table 3). For one analysis, Missing Week 12 eGFR data are imputed according to Section 5.6.1.2.

The difference between bardoxolone methyl and placebo in change from baseline of eGFR is estimated along with the 95% confidence interval at Week 12.

### **7.5. Secondary Efficacy Endpoint**

#### **7.5.1. Primary Analysis of the Secondary Endpoint**

The secondary endpoint of this study is the change in eGFR at Week 12 by CKD etiologies (Diabetes, Hypertension, and Other). The change from baseline eGFR for patients treated with bardoxolone methyl is compared with placebo at Week 12 by CKD etiology using mixed models repeated measures (MMRM) analysis as defined in Section 7.4.1.

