## 12. STATISTICS

### 12.1. Sample Size

With 70 patients enrolled (35 in each group), the study will have approximately 80% power to detect a difference between the two treatment groups in change from baseline in eGFR of 5.9 mL/min/1.73 m^2 for the primary endpoint at Week 12. The power calculation, which was based on a two-sided two-sample t-test, assumes the following:

- Two-sided Type I error rate of 0.05;
- Standard deviation of change from baseline in eGFR of 8 mL/min/1.73 m^2;
- A change from baseline in eGFR of approximately 5.9 mL/min/1.73 m^2;
- 15% drop-out and missing data will not be imputed.

Analysis of the primary endpoint will be based on the intent-to-treat (ITT) population and analyzed using mixed-model repeated measures (MMRM) with an unstructured covariance structure. The analysis method is expected to have at least as much power as the two-sample t-test used for study planning. Appropriate sensitivity analyses of the primary analysis will be specified in the Statistical Analysis Plan (SAP). The secondary efficacy endpoint will be tested for sufficiently large subgroups, but the study is not powered to show efficacy in the secondary efficacy endpoint.

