### **12.3.1. Primary Analysis of Efficacy**

The ITT population, which includes all enrolled patients, will be used as the population for assessment of the primary efficacy endpoint.

The primary endpoint is change in eGFR at Week 12. A mixed-model repeated measures (MMRM) model will be used to compare patients randomized to bardoxolone methyl to patients randomized to placebo. The model will include change from baseline in eGFR as the dependent variable, baseline eGFR and CKD stage as covariates, patient as a random effect, and the following fixed factors: treatment group, protocol-scheduled nominal time point, and the interaction between treatment and time. Other covariates may be specified in the SAP. Time ordering is a repeated measure within patients. It is assumed that errors for different patients are independent with an unstructured covariance structure. Missing data will not be imputed for the primary analysis since all data collected will be included in the MMRM analysis. Appropriate sensitivity analyses will be performed and defined in the SAP. The secondary efficacy endpoint will be tested for sufficiently large subgroups, but the study is not powered to show efficacy in the secondary efficacy endpoint. Exploratory efficacy will be summarized descriptively.

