#### 2.1.2. Secondary Objective

- To characterize the eGFR response at Week 12 across different etiologies of Chronic Kidney Disease (CKD).

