### 7.3. Subgroup Analysis

The off-treatment efficacy endpoints, the primary efficacy endpoint and secondary efficacy endpoint, will be descriptively analyzed for subgroups of interest to assess the general consistency of results across subgroups.

The following subgroup analyses are tabulated:

- Sex: female; male
- Ethnicity: Non-Hispanic/Latino; Hispanic/Latino
- Race: White; Non-White
- Baseline BMI ( $\text{kg}/\text{m}^2$ ):  $< 30$ ;  $\geq 30$
- Baseline eGFR ( $\text{mL}/\text{min}/1.73 \text{ m}^2$ ):  $< 30$ ;  $30-45$ ;  $\geq 45$
- Baseline eGFR ( $\text{mL}/\text{min}/1.73 \text{ m}^2$ ):  $< 45$ ;  $\geq 45$
- Baseline UACR ( $\text{mg}/\text{g}$ ):  $\leq 300$ ;  $> 300$
- Family history of CKD: Yes; No
- Kidney Etiologies (Diabetes, Hypertension, and Other)
- KDIGO Stratification: CKD progression risk heat map: yellow/orange; red/dark red
- Patients with IP Interruptions (Yes/No)

Subgroup analyses will include nominal significance levels for descriptive purposes only. The model used for subgroup analyses is the same as the primary analyses (Section 7) with additional terms of subgroup and subgroup-by-treatment.

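### No planned analysis gives a Week 12 contrast between CKD etiologies, although the secondary objective is about response across them

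*SAP*

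**What the plan says.** The secondary objective in SAP 2.1.2 is "To characterize the eGFR response at Week 12 across different etiologies of Chronic Kidney Disease (CKD"). SAP 7.5.1, headed as the primary analysis of that endpoint, names three groups (diabetes, hypertension, other) and says the drug arm "is compared with placebo at Week 12 by CKD etiology using mixed models repeated measures (MMRM) analysis as defined in Section 7.4.1". The fixed factors in 7.4.1 are KDIGO stratum, treatment, visit and treatment-by-visit. SAP 7.5.1.1 sends the sensitivity analysis to the ANCOVA of 7.4.1.1, which contains only KDIGO stratum and treatment.

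SAP 7.3 lists "Kidney Etiologies (Diabetes, Hypertension, and Other") among the subgroups for the primary, secondary and off-treatment endpoints. It adds subgroup and subgroup-by-treatment terms to the primary model. It also says: "Subgroup analyses will include nominal significance levels for descriptive purposes only".

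Protocol 12.3.1 says: "The secondary efficacy endpoint will be tested for sufficiently large subgroups". It gives no size threshold and adds that the study is not powered for this endpoint. SAP 5.1 makes significance levels nominal for endpoints outside 7.4, while still calling p<0.05 statistically significant. Under SAP 1.2, the SAP governs where the two documents differ.

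**The concern.** Describing a response across etiologies calls for the size of the differences between them, with intervals. The lead analysis supplies only effects within etiologies. Its wording is most naturally read as three separate fits, although the SAP does not say so. The 7.3 model does hold an etiology-by-treatment term. Without a subgroup-by-treatment-by-visit term, however, that term is one shift in the treatment effect common to all on-treatment visits, including those during dose titration. It is not the Week 12 difference.

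A reader left with three nominal p-values will tend to compare them. In groups this small, a uniform benefit can easily appear as significant in one etiology and not in another, and so be reported as an etiology-specific effect.

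Separate fits carry a further risk. An unstructured matrix over six visits has 6 × 7 / 2 = 21 parameters, to be estimated from about 70 / 3 ≈ 23 enrolled patients. If some fits fail, the fallback sequence in 7.4.1 could leave the three etiologies analysed under different covariance structures.

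**Working it through.** **Inputs.** Protocol 12.1 gives: "With 70 patients enrolled (35 in each group), the study will have approximately 80% power to detect a difference"; "Two-sided Type I error rate of 0.05"; "A change from baseline in eGFR of approximately 5.9 mL/min/1.73" m²; SD 8; and 15% drop-out. The etiology split is not given. Protocol 7.1 caps each of the three groups at about 40%, so each must exceed about 100 − 40 − 40 = 20%. Randomization is stratified by KDIGO risk only. Equal arms within each etiology are therefore an assumption, and a favourable one.

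**Step 1: reproduce the plan's power.** Evaluable patients per arm = 35 × 0.85 = 29.75. Two-sided two-sample t-test power for difference 5.9 and SD 8 is 79.9%, which matches the stated 80%.

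**Step 2: power within one etiology, equal thirds.**
- n per arm = 29.75 / 3 = 9.92
- SE = 8 × √(2 / 9.92) = 3.59
- noncentrality = 5.9 / 3.59 = 1.64, with df = 17.8 and critical t = 2.10
- power = 34.3%

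**Step 3: pattern of nominal significance when all three true effects are 5.9.**
- all three significant: 0.343³ = 4.0%
- none significant: 0.657³ = 28.4%
- mixed: 100 − 4.0 − 28.4 = 67.6%

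Simulation with 10 per arm per etiology agrees at 68%.

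**Step 4: vary the assumptions.** All rows use 15% loss and an identical true effect in every etiology.

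| Split | Effect | SD | Power per etiology | Mixed |
|---|---|---|---|---|
| 40/30/30 | 5.9 | 8 | 41/31/31% | 67.8% |
| 40/40/20 | 5.9 | 8 | 41/41/21% | 68.6% |
| equal | 5.9 | 6 | 54% | 74% |
| equal | 5.9 | 10 | 24% | 54% |
| equal | 4 | 8 | 18% | 45% |
| equal | 9.5 | 8 | 71% | 62% |
| equal | 9.5 | 6 | 92% | 23% |

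If only two etiologies of this size were tested under the protocol's size condition, mixed results would occur in 2 × 0.343 × 0.657 = 45%.

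**Step 5: is the choice of model the cause?** With the variance pooled over etiologies, the simulated mixed rate is still 68%. The cause is group size. Under identical effects the expected gap between the largest and smallest etiology estimate is 6.1, about the size of the planned effect.

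**Step 6: what a between-etiology contrast can show.**
- SE of a difference between two etiology effects = 3.59 × √2 = 5.08
- 95% half-width = 2.005 × 5.08 = 10.2
- difference detectable with 80% power = (1.96 + 0.84) × 5.08 = 14.2
- the 2-df interaction test rejects in 5% of simulated trials when the effects are equal, and in about 20% when they are 5.9, 5.9 and 0

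All of this uses t-test approximations to the Week 12 MMRM contrast.

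**The case against.** The case on the other side is substantial, and it disposes of several stronger readings.

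- *A reader might infer that the plan does not say which analysis leads.* It does. The heading of 7.5.1 names it as primary, and 7.3 is a descriptive consistency check.
- *A reader might infer that one set of p-values is a formal test and the other is not.* The word for testing is the protocol's. SAP 7.5.1 speaks of comparison, the SAP governs, and SAP 5.1 makes both sets nominal.
- *A reader might blame the mixed results on having two models.* Step 5 shows otherwise. Pooling leaves the rate unchanged, so only the interpretation statement in the fix addresses it.
- *A reader might want the interaction test to decide the question.* With about 20% power against effects of 5.9, 5.9 and 0 it would decide little, and a non-significant result could be misread as similarity. Setting 68% against its 5% error rate is also not like for like, because neither document uses the pattern of p-values as a decision rule.

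It is also fair to say that the objective is only to characterize, that the endpoint is worded by etiology, and that the lack of power is disclosed. SAP 7 places further model detail in a programming conventions document that is not available here.

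One gap remains: nothing in the protocol or SAP specifies a Week 12 difference between etiologies. Disclosing low power for efficacy does not supply one.

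**Conclusion.** The point holds as a cheap improvement to the SAP. The lead analysis is clear, but it lacks the between-etiology contrast that the objective calls for, and the 7.3 interaction as worded does not provide one at Week 12. At the planning values with an even split, identical effects would give mixed nominal significance in about 68% of trials, and splits within the 40% cap barely change this. The figure depends on the effect and SD: it is about 45% for an effect of 4 with SD 8, and 23% for 9.5 with SD 6. It is therefore not a general rule that equal effects will look different. It also rests on the assumed split, equal arms within etiology, and the t-test approximation. The endpoint is nominal and acknowledged to be unpowered, so the risk is misreading of the results; the primary analysis is not affected.

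**What to change.** In SAP 7.5.1, fit one MMRM to all ITT patients with the 7.4.1 terms plus ETIOLOGY, ETIOLOGY x TRT, ETIOLOGY x VISIT and ETIOLOGY x TRT x VISIT. From that model:

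- Report the three Week 12 treatment effects and the differences between them, each with a 95% confidence interval.
- Give the 2-df Week 12 interaction as a supportive, low-powered statistic, not as a deciding test.
- State that significance in one etiology and not another is not evidence of a difference, and that a non-significant interaction is not evidence of similarity.

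In 7.5.1.1, use a single ANCOVA with etiology and treatment-by-etiology terms. In 7.3, keep etiology for the off-treatment endpoints and refer to 7.5.1 for Week 12. Deleting it from 7.3 would also drop the planned off-treatment analysis by etiology, and possibly a safety breakdown, since SAP 9 draws on the same list.

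The cost is SAP wording and one re-specified model, with no new data or patients. The downsides are an assumed common covariance matrix across etiologies and imprecise differences, with a 95% half-width of about 10 mL/min/1.73 m².

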#### **7.5.1.1. Sensitivity Analysis of the Secondary Endpoint**

Sensitivity analysis of the secondary endpoint by treatment group and etiology is run according to Section [7.4.1.1](#).

## 8. EXPLORATORY EFFICACY

The following data summaries and analyses are presented for the ITT analysis set. Additional sensitivity analyses may be performed as appropriate.

All data values within the appropriate visit windows contribute to the analysis.

All analyses use ITT population.

### 8.1. Exploratory Efficacy Endpoint

#### 8.1.1. Off-Treatment MMRM eGFR Analysis

The exploratory endpoint of this study is the change in eGFR at Day 3, 7, 14, 21, 28, and 35 during the Off-Treatment portion of the study. The change from baseline eGFR for patients treated with bardoxolone methyl is compared with placebo at Day 3, 7, 14, 21, 28, and 35 using mixed models repeated measures (MMRM) analysis with the following fixed factors: KDIGO strata (HEAT\_STRAT), treatment group (TRT), time (i.e., VISIT; analysis visit number), and the interaction between treatment and time (TRT x VISIT).

The MMRM analysis uses all eGFR values collected from Week 12 to Week 17 according to off-treatment analysis visits 3,7,14,21,28, and 35 (Section [5.5.3.1](#)). An unstructured covariance matrix is used. Baseline value is original On-Treatment baseline value.

1. In the event the MMRM model with an unstructured covariance structure does not converge, the covariance structures are substituted as defined in Section [7.4.1](#).

##### 8.1.1.1. Sensitivity Analysis of Off-Treatment eGFR analysis – No Imputation for Missing Data

The change from baseline eGFR for patients treated with bardoxolone methyl is compared with placebo using ANCOVA analysis with the following fixed factors: KDIGO strata (HEAT\_STRAT) and treatment group (TRT).

The ANCOVA analysis uses eGFR values collected in each off-treatment visit (3,7,14,21,28, and 35) analysis window ([Table 4](#)). Missing eGFR data per visit are not imputed.

The difference between bardoxolone methyl and placebo in change from baseline of eGFR is estimated along with the 95% confidence interval at each off-treatment visit (3,7,14,21,28, and 35).

##### 8.1.1.2. Sensitivity Analysis of Off-Treatment eGFR Analysis – Imputation for Missing Data

The change from baseline eGFR for patients treated with bardoxolone methyl is compared with placebo using ANCOVA analysis with the following fixed factors: KDIGO strata (HEAT\_STRAT) and treatment group (TRT).

The ANCOVA analysis uses eGFR values collected in each off-treatment visit (3,7,14,21,28, and 35) analysis window ([Table 4](#)). For one analysis, Missing eGFR data per off-treatment visit are imputed according to Section [5.6.1.2](#).

The difference between bardoxolone methyl and placebo in change from baseline of eGFR is estimated along with the 95% confidence interval at each off-treatment visit (3,7,14,21,28, and 35).

### **8.1.1.3. Off-Treatment MMRM eGFR Analysis for Week 12 and Week 17 Completers**

Analyses will be conducted as described in Section 8.1.1 for patients who have completed 12 weeks of treatment and have off-treatment eGFR values collected within each of the analysis visit windows through Week 17 (Table 4).

### **8.1.1.4. Off-Treatment ANCOVA eGFR Analysis for Week 12 and Week 17 Completers**

Analyses will be conducted as described in Section 8.1.1.1 for patients who have completed 12 weeks of treatment and have off-treatment eGFR values collected within each of the analysis visit windows through Week 17 (Table 4).

### **8.1.1.5. Off-Treatment Non-linear Mixed Model**

A series of nonlinear mixed models will be used to fit the off-treatment eGFR change from baseline results for the Bardoxolone Methyl treated subjects. The modelling is to examine the behavior of eGFR among treated subjects once treatment is discontinued. Initially, the following model will be fit to the data:

$$Y_{ij} = \beta_{0i} + \beta_{1i} * \exp(\beta_{2i} * t_{ij}) + e_i,$$

where  $Y_{ij}$  denote the eGFR value for the  $i^{\text{th}}$  subject at the  $j^{\text{th}}$  timepoint,  $\beta_{0i}$  is the asymptote,  $\beta_{1i}$  is referred to as the amount,  $\beta_{2i}$  is referred to as the decay rate,  $t_{ij}$  denotes the time for the  $i^{\text{th}}$  subject at the  $j^{\text{th}}$  timepoint, and  $e_i$  denotes the error term. In the model where all effects are fixed, the  $\beta$ s are defined as follows:

- $\beta_{0i} = \beta_0$
- $\beta_{1i} = \beta_1$
- $\beta_{2i} = \beta_2$

The random effects are introduced into a sequence of models as described below:

- 1) First a random effect for  $\beta_{0i}$  will be introduced and defined as  $\beta_{0i} + U_{0i}$ , where  $U_{0i}$  is the random effect.
- 2) The second model to be fit will include a random effect for both  $\beta_{0i}$  and  $\beta_{1i}$ , with the random effect for  $\beta_{1i}$  is defined as  $\beta_{1i} + U_{1i}$ .
- 3) The third model to be fit will include a random effect for all three coefficients, with the random effect defined as  $\beta_{2i} + U_{2i}$ .

Each additional random effect will be added to the model if the model is stable. The Akaike information criteria will be used to select the final model (lower is better). If none of the non-linear mixed models converge, other models may be implemented such as a quadratic model.

**8.1.2.**

[REDACTED]

## 9. SAFETY AND TOLERABILITY

Safety and tolerability are evaluated by AEs, SAEs, clinical laboratory test results, body weight, vital signs, 12-lead ECG findings, and physical examination. All analyses of the safety data are performed using the safety analysis set. Descriptive statistics are presented by treatment group assignment in the safety analysis set. No formal statistical testing is performed for safety analyses. Safety is also summarized by a portion of the subgroups defined in Section 7.3. On-treatment values are summarized according to the analysis study windows in Section 5.5.3; off-treatment values are summarized according to the analysis study windows in Section 5.5.3.1. Safety data summaries are grouped by treatment.

Continuous safety parameters (including selected clinical chemistries and vital signs) may be summarized using the methodology described in Section 9.5.1 and Section 9.6. Only the visit windows outlined in Section 5.5.1 are included in these analyses.

### 9.1. Adverse Event Preferred Term and Body/Organ System Summary Tables

Treatment-emergent adverse events (TEAEs) are summarized by treatment as defined by the safety analysis set.

Treatment-emergent adverse events (TEAEs) are events that either:

- Have a date of onset on or after the date of first dose and not more than 30 days after the date of the last dose of study drug, or
- Have no recorded date of onset with a stop date after the first dose of study drug, or
- Have no recorded date of onset or stop date.

General considerations for TEAE summaries are:

- Multiple events by preferred term (PT) and system organ class (SOC) are counted once only per patient for summaries of TEAE incidence.
- For summaries of TEAE incidence by severity, only the most severe event is counted per patient.
- For summaries of TEAE incidence by relationship, only the most related event is counted per patient.
- A TEAE with a missing resolution date or incomplete date that is not identified as continuing is assumed to be continuing.
- For summaries of the number of TEAE events, all TEAEs are counted.
- Withdrawal TEAEs include the subset of TEAEs that started one to 30 days after the last dose of study drug.

Off-treatment AEs are events with a start date more than 30 days after last dose and not considered treatment emergent. Off-treatment AEs will be summarized separately.

AEs are coded using MedDRA (Medical Dictionary for Regulatory Activities) version 21.1. In MedDRA, each verbatim term is mapped to a preferred term and high level term (HLT), which is then mapped to a system organ class (SOC).

The investigator grades the severity of the AEs as mild, moderate, or severe as defined in the study protocol. The investigator grades association or relatedness to the study medication according to criteria specified in Section 11.4 of the protocol.

As defined in the protocol, a serious adverse event (SAE) is an adverse event (occurring at any dose and regardless of causality) that:

- Results in death;
- Is life-threatening;
- Requires inpatient hospitalization or prolongation of existing hospitalization;
- Results in persistent or significant incapacity or substantial disruption of the ability to conduct normal life functions;
- Is a congenital anomaly or birth defect in an offspring of a patient taking study drug;
- Is an important medical event.

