Patients in the study will follow the same visit and assessment schedule. Patients will be assessed during treatment at Day 1, Weeks 1, 2, 4, 6, 8, and 12 and by telephone contact on Days 3, 10, 21, 31, 35, and 45. Date of last dose and the end-of-treatment assessments mark the end of the treatment period. Patients will not receive study drug during a 5-week off-treatment period between Weeks 12 and 17 (Figure 1).

[figure not shown]
The off-treatment (OT) period includes 5 visits requiring various assessments to characterize eGFR from the time of study drug discontinuation through Day 35 off-treatment. Patients will be assessed on Day 3 OT, Day 7 OT, Day 14 OT, Day 21 OT, Day 28 OT, and Day 35 OT. The OT day corresponds to days after last dose. Day 1 OT is the first day after receiving the last dose. Any patient who permanently discontinues study treatment early will follow the same OT assessment schedule.

All patients, including patients who discontinue treatment early, should complete the end-of-study (EOS) visit 17 weeks after randomization.

All efforts should be made to follow all randomized patients for the full OT period of the trial, and the EOS visit (Week 17), including patients who discontinue drug early.

Final analysis of the primary efficacy endpoint will occur after all enrolled patients have completed their Week 17 visit (or have terminated from the trial).

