### 7.6.3. Treatment Period (From Day 1 through Week 12)

The Treatment Period includes 13 visits (clinic and phone visits). During the Treatment Period, in clinic visits generally have a window of  $\pm 3$  days, and phone visits generally have a window of  $\pm 2$  days. Careful attention should be paid to visit windows beginning with the Week 12/EOT visit, which contains only a “minus” window (i.e., Week 12 should occur on Day 84–3 days). Out of window visits will result in protocol deviations.

During the Treatment Period, dose titration should be completed as outlined in Section [7.4.1](#).

The Treatment Period concludes at the Week 12/EOT Visit. **Patients should be instructed to refrain from taking IP on the day of the Week 12 visit. The last dose of study drug should be the day prior to the Week 12 visit.**

Labs obtained at this visit are important from an endpoint perspective, as they provide the final on-treatment eGFR values.

For detailed information on the Day 1 visit, see Section [7.6.2](#).

For detailed information on the Week 12 visit, see Section [7.6.4](#).

Treatment Period clinic visits between Day 1 and up to Week 12 (Week 1, Week 2, Week 4, Week 6, and Week 8) must include the following assessments:

- Review and record concomitant medications
- Review and record AEs
- Perform vital sign assessments (sitting blood pressure, pulse, heart rate, temperature, and weight) as outlined in Section [9.10.10](#)
- Dispense weight and IP diary and train patient on proper diary entry for recording daily weight and IP administration (Day 1, Week 2, Week 4, Week 6, and Week 8)
- Collect/review weight and IP diary (Week 1, Week 2, Week 4, Week 6, and Week 8)
- Perform a targeted physical examination, if needed
- Perform urine pregnancy test, if applicable
- Dispense study drug based on bottle number or kit number obtained from RTSM and instruct patient on proper administration of study drug (Day 1, Week 2, Week 4, Week 6, and Week 8)
- Collect and review study drug (Week 2, Week 4, Week 6, and Week 8)
- Perform a buccal swab (cheek swab) for genetic testing (at any visit between Day 1 and the EOS visit)

- Collect blood and urine for clinical laboratory tests:
  - Clinical chemistry, including eGFR
  - BNP and NT-proBNP
  - Hematology
  - Urinalysis and microscopy
  - Urine for UACR – first morning void specimen (Week 4 and Week 8)
  - Liver and Kidney Injury Biomarkers (Week 6)
  - C-Reactive Protein (Week 6)
  - PT/INR (Week 6)

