### 5.2. General Post Text Summary Table and Individual Subject Data Listing Format Considerations

Unless otherwise specified, descriptive statistics for continuous variables include the number of patients with data (N), mean, standard deviation (SD), median, minimum, and maximum. The same number of decimal places as in the observed value are presented when reporting minimum and maximum; 1 more decimal place than in the observed value is presented when reporting mean and quartiles; and 2 more decimal places than in the observed value is presented when reporting SD.

Categorical data are presented using frequency counts and percentages. All percentages are rounded to 1 decimal place, unless otherwise specified. Percentages equal to 100 are presented as 100% and no percentages are presented for zero frequencies. Where individual variable values are missing, summaries of categorical data are based on reduced denominators (i.e., the denominators include only patients with available data) and the number of missing values is presented. For summaries of AEs and concomitant medications (CM), the percentages are based on the total number of patients in each treatment group.

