## **5.5. Derived and Transformed Data**

### **5.5.1. Study Day**

Study day is the day relative to the date of randomization. Day 1 is defined as the date of randomization. Assessments that occur after randomization but before the first dose of study drug are considered to occur on study Day 1.

Assessments without timestamp collected on the same date as the first date of study drug administration are considered to occur before the first dose of study drug administration.

For visits (or events) after randomization, day is calculated as:

- Study day = visit (or event) date - date of randomization + 1

For visits (or events) before randomization, day is calculated as:

- Study day = visit (or event) date - date of randomization

The quantity ‘days since first dose’ is defined as:

- days since first dose = visit (or event) date – date of first dose + 1

The quantity ‘days since last dose’ is defined as:

- days since last dose = visit (or event) date - date of last dose

For summaries that present distribution of time expressed in weeks and months, weeks are defined as days divided by seven and months as days divided by 30.4.

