### **9.1.2. Summaries of Adverse Events**

TEAEs and OTAEs are summarized by treatment based on year of AE onset and overall. For each treatment, SOC, and PT, the number and percentage of patients reporting an event is calculated. In summary tables, SOC is presented alphabetically and events within each SOC are presented by decreasing frequency count.

Summary tables (number and percentage of patients and events) of TEAEs (by SOC and PT) are provided by treatment as follows:

- All TEAEs
- All related TEAEs (definitely, probably, or possibly related)
- All TEAEs by severity
- All serious TEAEs (including deaths)
- All non-serious TEAEs
- All related serious AEs (including deaths)
- All TEAEs leading to permanent discontinuation of study drug
- TEAEs by time to onset ( $\leq 12$  weeks and  $>12$  weeks)
- TEAEs exhibited in  $>5\%$  of patients

Listings are provided showing:

- All AEs
- Deaths
- Serious adverse events
- AEs leading to permanent discontinuation of study drug
- AEs leading to de-escalation of study drug

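### Off-treatment AE percentages mix about 5 days at risk for completers with up to 88 for early stoppers, so the arms are not comparable if stop rates differ

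*SAP*

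**What the plan says.** SAP 9.1 divides AEs by time since last dose. An event with a known onset date is treatment-emergent (TEAE) if it starts on or after first dose and "not more than 30 days after the date of the last dose of study drug". After that, "Off-treatment AEs are events with a start date more than 30 days after last dose and not considered treatment emergent". SAP 5.5.1 sets the count: "days since last dose = visit (or event) date - date of last dose". The first day on which an OTAE can start is therefore day 31.

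SAP 9.1.2 brings OTAEs under the same summary as TEAEs: "TEAEs and OTAEs are summarized by treatment based on year of AE onset and overall", and "For each treatment, SOC, and PT, the number and percentage of patients reporting an event is calculated". SAP 5.2 fixes the denominator: "For summaries of AEs and concomitant medications (CM), the percentages are based on the total number of patients in each treatment group".

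Follow-up is tied to randomization instead. Protocol 11.2.1.1 collects AEs from first dose to the final visit. Protocol 7.1 says: "All patients, including patients who discontinue treatment early, should complete the end-of-study (EOS) visit 17 weeks after randomization". For completers, Protocol 7.6.3 says: "The last dose of study drug should be the day prior to the Week 12 visit", and their final visit is OT Day 35. For early stoppers, footnote a of Protocol Table 4 and Protocol 8.3.1 add a separate final visit about 17 weeks after randomization.

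For OTAEs, neither document plans person-time, a time-to-event summary or a common window after last dose.

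**The concern.** The OTAE window opens at a time set by last dose and closes at a time set by randomization. Its length therefore depends on when the patient stopped drug. A patient with almost no time at risk and a patient with two months of it each count as one in the denominator, so the percentage reflects stopping pattern as well as event rate.

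Safety and tolerability is a primary objective, and SAP 9 plans no formal safety tests. Readers will judge by setting the displayed percentages side by side. Unequal stopping is plausible: the protocol describes nausea, muscle spasms, fluid retention and aminotransferase rises with the drug, and Protocol 9.1.2 has permanent stopping rules for the last of these. An excess of OTAEs could then be read as late harm when it comes from longer observation.

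**Working it through.** The documents state no days-at-risk figure, so there is none to reproduce.

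**Inputs from the documents.** The window opens on day 31 after last dose (SAP 9.1, 5.5.1). The Week 12 visit falls on Day 81 to 84, with last dose the day before (Protocol 7.6.3, 7.6.4). A completer's final visit is OT Day 35 and an early stopper's is Week 17, taken as Day 17 × 7 = 119. There are 35 patients per arm (Protocol 12.1), all assumed dosed.

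**Assumptions.** Stop rates and stop days by arm, an equal daily AE rate in both arms, and full follow-up to the final visit.

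**Days at risk per patient** = day of final visit − day of last dose − 30.
- Completer: 35 − 30 = 5 days. A final visit between OT Day 32 and 38 gives 2 to 8. Last dose on Day 83 with a final visit on Day 119 gives 6.
- Early stopper, final visit on Day 119:

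| Last dose | Days at risk |
|---|---|
| Day 56 | 119 − 56 − 30 = 33 |
| Day 42 | 119 − 42 − 30 = 47 |
| Day 35 (the Week 5 example in Protocol 8.3.1) | 119 − 35 − 30 = 54 |
| Day 28 | 119 − 28 − 30 = 61 |
| Day 14 | 119 − 14 − 30 = 75 |
| Day 1 | 119 − 1 − 30 = 88 |

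**Person-days per arm** = 35 × [p × d + (1 − p) × 5], where p is the share stopping and d is the stopper's days at risk.
- 20% vs 5% at Day 28: 35 × (12.2 + 4.0) = 567 vs 35 × (3.05 + 4.75) = 273. Ratio 2.08.
- 15% vs 5% at Day 42: 35 × (7.05 + 4.25) = 396 vs 35 × (2.35 + 4.75) = 248. Ratio 1.59.
- 15% vs 10% at Day 56: 35 × (4.95 + 4.25) = 322 vs 35 × (3.3 + 4.5) = 273. Ratio 1.18.

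**Expected events** in the first scenario, at an assumed 1 per 100 person-days: 5.7 vs 2.7. At 0.25 per 100: 1.4 vs 0.7.

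**Patients with an event**, the statistic SAP 9.1.2 reports, at 1 per 100 days (h = 0.01): p × (1 − e^(−61h)) + (1 − p) × (1 − e^(−5h)).
- 20% stopping: 0.2 × 0.457 + 0.8 × 0.0488 = 13.0%.
- 5% stopping: 0.05 × 0.457 + 0.95 × 0.0488 = 6.9%.
- Ratio about 1.9.

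Across assumed rates of 0.25 to 2 per 100 days, stop rates of 10–30% vs 5–10%, and 54 or 75 days for stoppers, this ratio runs from 1.23 to 2.95.

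**If every stopper leaves before day 31**, at the same rate: 0.8 × 0.0488 = 3.9% vs 0.95 × 0.0488 = 4.6%. The direction reverses. Over assumed rates of 0.25 to 2 per 100 days and 54 to 88 days for stoppers, following about 6–14% of stoppers to Week 17 is the break-even point.

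**TEAE tables.** The window lasts last-dose day + 30: 113 days for a completer with last dose on Day 83, and 58, 72 or 86 for stops at Day 28, 42 or 56. Mean days at risk in the three scenarios:
- 102.0 vs 110.3, ratio 0.93.
- 106.9 vs 111.0, ratio 0.96.
- 109.0 vs 110.3, ratio 0.99.

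**The case against.** OTAEs are a residual category. Both documents expect acute eGFR effects to resolve within 10 to 14 days of stopping. SAP 9.1 already defines a common window for events soon after stopping: withdrawal TEAEs, which start 1 to 30 days after last dose. The tables are descriptive. SAP 6.1 and 9.2 report discontinuations, status by visit and duration of exposure, and SAP 9.1.2 lists every AE, so an imbalance in stopping would be visible. Expected counts are small.

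All of this stands, and it keeps the point minor. It does not make the OTAE percentages comparable. The exposure summary covers days on drug rather than days at risk after it, and the time-to-onset table covers TEAEs only.

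A reader might infer three stronger things that the documents do not support:
- **That the arm with more stops will necessarily look less safe.** This needs unequal stopping, of which the documents give no figures by arm, and stoppers who remain in follow-up past day 30. In addition, Protocol 9.1.9 limits follow-up after dialysis or transplant to vital status and SAEs, so non-serious OTAEs do not arise there.
- **That the TEAE tables are distorted to a similar degree.** The shift in mean days at risk is about 1–7%. The protocol also describes the known effects as early: fluid overload in about the first four weeks, aminotransferase peaks two to four weeks after starting or a dose increase, muscle spasms mostly in the first two months. If all events fell by Day 28 equally in both arms, a TEAE person-time rate would make the 20%-stop arm look about 8% worse (110.3 / 102.0 = 1.08).
- **That a hypothesis test is affected.** No safety test is planned.

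**Conclusion.** The point holds for the OTAE summary, conditionally, as a minor matter of presentation. That time at risk runs from about 5 days for a completer to as many as 88 for an early stopper follows from the documents' own rules, and nothing planned corrects for it. Any distortion between arms depends on assumptions: with equal daily rates and follow-up to Week 17, expected events differ by a factor of about 1.2 to 2.1 in the three scenarios shown. With equal stopping (same rates and timing) there is none, and if nearly all stoppers leave before day 31 it runs the other way. The effect is on how a descriptive table is read.

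**What to change.** In SAP 9.1.2, add three items by arm to the OTAE summary, beside the existing counts and percentages:
- the number of patients still followed beyond day 30 after last dose;
- person-days at risk, from last dose + 31 to last contact;
- OTAEs per 100 person-days.

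For non-serious events, person-time should end at dialysis or transplant, because only SAEs and vital status are followed after that. The TEAE tables need no change on this account.

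The cost is a short SAP edit and a few table entries from dates already collected. Rates from a handful of events are imprecise, so the counts should stay. The rate also treats days 31 to 35 in completers and later days in stoppers as equivalent, which a table footnote should say.
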